## **9. Unblinding**

In the event of a medical emergency where knowledge of the participant's blinded treatment is critical to their medical management, the blind may be broken by the investigator. Before breaking the blind, the investigator must determine whether or not knowledge of the blinded information will alter the immediate care of the participant. In some instances, it may be possible to

treat the participant by assuming they are receiving active product. The investigator will discuss the decision to unblind with the DSMB. Blinding will only be broken for appropriate medical reasons such as managing treatment of a patient in an emergency or if required for reporting to regulatory authorities. Any event for which the study blind is broken will be reported as an SAE. The accompanying SAE report should include a comment about breaking the blinding.

Figure 1. Overview of Study Design

## D. Follow-up

**Parent Evaluation Time Points:** After randomization, the study team will provide the study drugs, study drug application instruction sheets and informational material. All participants will begin the 5-day treatment course at that time. During the 5-day treatment period, a study team member will contact the study participant daily at the bedside, on the phone, by email or by text message to assess compliance with treatment and to answer any questions. When available, parent(s) will be re-tested for colonization at 2-week intervals from randomization for the first 8 weeks and then every four weeks until discharge. Follow up swabs may be taken within a week of scheduled time points, based on participant availability. Anatomic sites to be tested and frequency of testing are detailed in Table 1. Peri-anal swabs will only be collected at enrollment and final screening. The final visit and testing will be performed at the time of a neonate's discharge from the NICU or at the time the child is identified to have acquired *S. aureus*.

**Neonate Evaluation Time Points:** After informed consent and randomization of parents, the neonate will undergo baseline testing to determine baseline *S. aureus* colonization status. This testing will occur on study day 1, the same day that parents begin treatment. Screening cultures will be performed by obtaining a swab from the following anatomical sites: anterior nares, the umbilicus, groin, and peri-anal area. If the nares site is not available to swab, the throat will be swabbed instead. Those neonates who test positive for *S. aureus* colonization at time of randomization will not be included in the primary analysis. After baseline testing, repeat testing will be performed every 7 days. Study samples will be saved and processed in the lab. The final visit and testing will be performed at the time of a neonate's discharge from the NICU.

Table 1

Frequency of Parent Swab Collection			
Site	Screening	Weeks 2, 4, 6, 8, 12, 16, 20, 24, 28,....	Time Neonate Acquires S. aureus
Nares	X	X	X
Throat	X	X	X
Groin	X	X	X
Peri-anal	X		X

Table 2

Frequency of Neonate Swab Collection			
Site	Parent Randomization	Weeks 1, 2, 3, 4,....	NICU Discharge
Nares	X	X	X
Umbilicus	X*	X*	X*
Groin	X	X	X
Peri-anal	X	X	X

\*Umbilicus will only be tested if the neonate has attached umbilical cord.

## **5. Primary and Secondary Endpoints and Outcomes**

### **A. Primary: Primary outcome is neonatal acquisition of *S. aureus* strain that is concordant to parental *S. aureus* strain as determined by periodic surveillance cultures or a culture collected during routine clinical care that grows *S. aureus*.**

Acquisition will be defined as meeting two criteria:

- 1) A neonate who had baseline surveillance cultures that were negative for *S. aureus*
- 2) A neonate who has a subsequent surveillance culture or culture collected during routine clinical care that grows *S. aureus*.

Concordant strains must meet the following criteria:

- 1) Strains that are related using pulsed-field gel electrophoresis (PFGE) analysis, as described below. Isolates will be considered related if their patterns have  $\leq 3$  band differences. Isolates with  $>3$  band differences will be considered epidemiologically different strain types. A neonate who has a subsequent surveillance culture or culture collected during routine clinical care that grows *S. aureus*.
- 2) Alternative typing methods will be used to further discriminate highly prevalent strains or those that are not typable by PFGE.
- 3) The same strain from the initial parent screening is identified from the neonate.

**Primary outcome ascertainment** – We will measure each neonate's baseline *S. aureus* colonization status at the time of study enrollment. As described above, neonates will then have swabs collected weekly after enrollment and at time of discharge from multiple anatomic sites by a study team member. We also will use data from cultures collecting during routine clinical care in the NICU. These cultures include cultures of nasal swabs collected every Tuesday as part of an active *S. aureus* surveillance program and other cultures collected during routine clinical care (e.g. blood cultures, respiratory cultures, wound cultures, etc.). Cultures collected by the study team and cultures collected during routine clinical care will both be used to identify *S. aureus* acquisition in neonates. Of note, nasal surveillance swabs collected as part of the hospital surveillance program are plated on selective media plates to detect *S. aureus* colonization, as previously reported [1].

**Reducing the risk of bias in outcome ascertainment:** Clinicians will continue to send cultures to evaluate neonates for possible infection as part of routine clinical management. The primary care providers in the NICU will not participate in the study and will be masked to the parent-neonate pair assignment. Maintaining masking of the clinicians will reduce the chance that practices for obtaining clinical cultures will differ between the two groups.

The **observation period, or survival time**, is the time that a neonate is at-risk of concordant *S. aureus* acquisition. We will calculate survival time as 1) the interval

between randomization and the date of final culture (either at time of final surveillance culture or at time of discharge culture) for neonates who did not acquire concordant *S. aureus* and 2) the interval between randomization and date of first positive culture for neonates that acquire concordant *S. aureus*.

**B. Secondary outcomes of interest include:**

**1. Neonatal acquisition of *S. aureus* as determined by periodic surveillance cultures or a culture collected during routine clinical care that grows *S. aureus*.**

Acquisition will be defined as meeting two criteria:

- 1) A neonate who had baseline surveillance cultures that were negative for *S. aureus*
- 2) A neonate who has a subsequent surveillance culture or culture collected during routine clinical care that grows *S. aureus*.

**Outcome ascertainment** – same as for primary outcome

**Observation period or survival time** – same as for primary outcome but does not require the *S. aureus* strain to match that of the parent.

**2. Neonatal *S. aureus* infection as determined by cultures collected during routine clinical care**

**A *S. aureus* infection** will be defined using criteria established by the Centers for Diseases Control and Prevention National Healthcare Safety Network and will be determined using results of cultures sent during routine clinical care (other than surveillance cultures).

**Secondary outcome ascertainment** - Two study team members that are blinded to treatment assignment will review all clinical cultures for *S. aureus* during the treatment and control period and determine if the culture represents an infection due to *S. aureus*. A third study team member will review the case in the event of discordant results.

The **observation period, or survival time, is the** time a neonate is at-risk of *S. aureus* infection. We will calculate survival time either by 1) the interval between randomization and the date the neonate is discharged from the NICU or death for neonates who did not develop a *S. aureus* infection or 2) the interval between randomization and date of positive culture for neonates that develop *S. aureus* infection. Neonates will not be included if they have an infection after meeting the primary outcome of concordant *S. aureus* colonization or the secondary outcome of neonatal acquisition of *S. aureus*.

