## **9. Statistical Analysis Plan**

### **A. Sample size and power estimates:**

The primary outcome will be time to concordant *S. aureus*-colonization. Time to concordant *S. aureus* colonization will be expressed using an indicator variable for concordant colonization and time to concordant colonization. The a priori assumed

control group concordant colonization rate is 10% and power calculations are based on the unadjusted Cox proportional hazards model where the primary covariate is the treatment group indicator. In time to event analyses, power is driven by the number of events; i.e. number of concordant colonizations. Given our assumed control group concordant colonization rate of 10%, 38 events are required to detect a 60 percent reduction in the hazard of concordant colonization (Hazard Ratio: HR 0.4) in the intervention group with 80% power and Type I error rate of 5%. The 38 events includes a roughly 2% inflation for pre-planned interim analyses (see Section 9.B). Given that we expect 5% of the parent-neonate pairs will be non-singleton births, we increased the number of required events to 40 to account for the possible clustering of concordant colonization among non-singleton neonates. Some neonates may test positive at baseline for *S. aureus* after randomization and will not be eligible for the analysis of the primary outcome. Similarly, if one neonate from a multiple gestation birth is positive for *S. aureus* at baseline and another neonate is not, then the negative infant will be eligible. Eligible parent-neonate pairs will be assigned to either treatment or control as a unit until 40 events are confirmed. Prior to the start of the study, given our *a priori* assumption of a 10% concordant colonization rate in the control group and a HR of 0.40, we anticipated recruiting 400 parent-neonate pairs to achieve the required 40 concordant colonizations. With 400 parent-neonate pairs, we have roughly 80% power to detect an absolute risk difference of at least 7% for the secondary analysis of the indicator of concordant colonization within 90 days after randomization.

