Planned analysis of secondary outcomes will include the following: a) Repeat the primary analysis where time to concordant colonization will not be censored at 90 days after randomization; time will be defined as the time from randomization to the first of concordant colonization or last available culture (clinical, surveillance or NICU discharge), b) Define the treatment effect as the difference in the proportion of neonates acquiring concordant *S. aureus* by 4 and 8 weeks after randomization comparing the Treatment to Control group; this treatment effect will be estimated by taking the difference in the observed proportions comparing the Treatment and Control groups with standard error estimates and confidence intervals derived from the bootstrap procedure described above, c) Using the methods described above, estimate the treatment effect on the acquisition of *S. aureus* (regardless of concordant status), treated as both time to acquisition and the binary indicator for any acquisition by 4 and 8 weeks, and d) Using the methods described above, estimate the treatment effect on neonatal *S. aureus* infection, treated as both time to infection and the binary indicator for infection by 4 and 8 weeks. For the analysis of the *S. aureus* infection, we will first consider only *S. aureus* infections that occur prior to a neonate being identified as acquiring *S. aureus* colonization. For example, if a neonate acquires *S. aureus* colonization and then has a subsequent infection 7 days later, this infection will not be included. Only clinical cultures that occur before or on the same day as the first positive surveillance culture will be

considered. The NICU has a policy to decolonize all *S. aureus* colonized neonates which will impact the risk of infection in those that are first identified as colonized. Despite the possible independent impact of neonate decolonization on *S. aureus* infection risk, we recognize the importance of reporting all *S. aureus* infections in study patients; therefore, we will repeat the analysis, including *S. aureus* infections that occur at any time during a neonate's admission in the NICU. Lastly, a descriptive analysis of neonate mortality and bloodstream infections will be conducted, estimating the rate of occurrence separately for each treatment group.

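### The first infection analysis ignores infections after colonisation but keeps colonised neonates at risk until discharge or death; if treatment lowers acquisition, this biases the infection hazard ratio modestly against treatment

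*Combined protocol and SAP*

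**What the plan says.** Section 5.B.2 describes survival time for infection as the "time a neonate is at-risk of" *S. aureus* infection. For neonates without an infection it runs as "the interval between randomization and the date the neonate is discharged from the NICU or death for neonates who did not develop" one. Nothing in the section ends this time at acquisition. The section then adds an exclusion: "Neonates will not be included if they have an infection after meeting the primary outcome of concordant" colonisation, or after any acquisition.

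Section 9.C takes infection as a planned secondary analysis, "treated as both time to infection and the binary indicator for infection by 4 and 8 weeks". Its first version is limited to infections that precede identified colonisation: "Only clinical cultures that occur before or on the same day as the first positive surveillance culture" are to count. Here the later infection is set aside, not the neonate. The reason given is that the NICU decolonises colonised neonates, which changes their later risk of infection. Section 9.C then commits to a repeat that counts infections at any time in the NICU stay.

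The cut-off events differ. Section 5.B.2 uses acquisition, and Section 5.B.1 lets a clinical culture establish it: "A neonate who has a subsequent surveillance culture or culture collected during routine clinical care that grows" *S. aureus*. Section 9.C uses the first positive surveillance culture.

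**The concern.** In the first analysis, numerator and denominator follow different rules. Once a neonate is colonised no later infection can count, yet the neonate stays in the Cox risk set until discharge or death. That time is not time at risk of the event being analysed. Acquisition is what the treatment is meant to reduce, so the surplus time would be larger in the control arm. The control infection rate would be diluted more, and the hazard ratio would move against treatment. The 4- and 8-week proportions under the same restriction move the same way, because more control infections are removed from the count.

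Separately, excluding a neonate for an infection after acquisition selects on a post-randomisation event. An analyst following Section 5.B.2 and one following Section 9.C would analyse different sets of neonates. Neither section names an estimand that treats acquisition as a competing event. Infection is one of the secondary hypotheses in Section 3.D, so its definition should be unambiguous.

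**Working it through.** **Plan's own figure.** The plan gives no rate or power for infection. Its figure for acquisition reproduces: 4(1.960 + 0.842)² / (ln 0.4)² = 4 × 7.849 / 0.8396 = 37.4, or 38.1 with the 2% interim inflation, against 38 stated in Section 9.A. An acquisition hazard ratio of 0.4 at a 10% control concordant rate is therefore the right starting point.

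**Formula.** Let the infection hazard before acquisition be λ in both arms (true hazard ratio 1.0), and let q be the fraction of an arm's total time that falls after acquisition. Counted infections are proportional to λ(1 − q), while the denominator is all time. The ratio as written is close to

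(1 − q_T) / (1 − q_C).

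If time ends at acquisition, the denominator is also (1 − q) and the ratio is 1. If acquisition is equal, q_T = q_C and the ratio is again 1.

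**Assumptions (not in the documents).** Stay of 5 days plus an exponential time with mean 30, capped at 90 days; constant acquisition hazard a; rare infection.

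- Mean total time: 5 + 30(1 − e^(−85/30)) = 33.24 days.
- Mean uncolonised time: U(a) = (1 − e^(−5a))/a + e^(−5a)(1 − e^(−85(a + 1/30)))/(a + 1/30), and the proportion acquiring is a × U(a).
- Control: a × U(a) = 0.10 gives a = 0.00326 per day, U = 30.64, q_C = 1 − 30.64/33.24 = 0.078.
- Treatment: 0.4a gives U = 32.16, q_T = 0.0325.
- Ratio: 0.9675 / 0.9220 = 1.049.

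Non-concordant acquisition is then added at an equal hazard in both arms, set so that it alone would give the stated percentage:

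| Non-concordant | q_C | q_T | Ratio as written | Control share of post-acquisition time |
|---|---|---|---|---|
| 0% | 0.0780 | 0.0325 | 1.049 | 0.71 |
| 10% | 0.1460 | 0.1063 | 1.047 | 0.58 |
| 30% | 0.2891 | 0.2605 | 1.040 | 0.53 |

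**Simulation of the same cases** (Cox model, 2 million neonates per arm, infection 2% per 30 days assumed):

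| Quantity | 0% | 10% | 30% |
|---|---|---|---|
| HR, later infections ignored (9.C) | 1.049 | 1.047 | 1.040 |
| HR, neonates infected later dropped (5.B.2) | 1.047 | 1.046 | 1.039 |
| HR, time ended at acquisition | 1.000 | 1.001 | 1.000 |
| HR, all infections counted | 1.000 | 1.000 | 1.000 |
| 4-week risk ratio, restricted | 1.024 | 1.023 | 1.022 |
| 8-week risk ratio, restricted | 1.039 | 1.038 | 1.034 |

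**Sensitivity.**

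- Mean exponential stay of 15 to 60 days, and acquisition timing from all in week 1 to increasing hazard: HR 1.02 to 1.06 at plan rates; 4-week risk ratio 1.00 to 1.05, 8-week 1.02 to 1.06.
- Separate calculation with other stay assumptions: 1.03 with fixed follow-up, 1.06 with exponential discharge. A true HR of 0.50 then reads 0.516 to 0.529.
- Control acquisition of 20% to 40% with the whole hazard halved: 1.06 to 1.27.

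**Against sampling error.** If the 3.7% background figure for very low birth weight infants (Section 2.A) held for 400 neonates, which is an assumption, infections would number 400 × 0.037 = 14.8. The standard error of the log hazard ratio is 2/√14.8 = 0.52, and the 95% interval factor is e^(1.96 × 0.52) = 2.8. The shift is ln(1.02)/0.52 = 0.04 to ln(1.06)/0.52 = 0.11 standard errors.

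**The case against.** The strongest reply is that the bias is immaterial: about a tenth of a standard error at most at plan rates, in one of two analyses of a secondary outcome, with an unaffected companion already planned. The size stands, and it is why this is a modest point. The companion does not repair the first analysis, and it does not settle who belongs in it.

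A second reply is that bias depends on the estimand. Keeping colonised neonates in the risk set gives a subdistribution-type hazard ratio with acquisition as the competing event, and the restricted 4- and 8-week proportions validly estimate the risk of infection not preceded by acquisition. These are legitimate quantities. However, the plan names neither, and its reason for the restriction, that decolonisation alters later risk, points to the hazard among neonates not yet colonised.

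Third, a colonised neonate is still at risk of infection in the ordinary sense. That is true, but not of an infection this analysis can count.

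Fourth, the two readings of the exclusion differ by only 0.001 to 0.002 in the hazard ratio. That is so under these assumptions, yet dropping randomised neonates for a later event still needs correcting.

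Finally, censoring at acquisition is only a partial cure if the same neonates are prone to both colonisation and infection. With an assumed shared gamma frailty of variance 1, the hazard ratio is 1.05 to 1.09 as written, 1.03 to 1.04 censored and 1.00 with all infections counted. This stands, and it is why the all-infections analysis should carry the total effect.

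**Conclusion.** The concern holds. The event rule and the time rule of the first infection analysis do not match, and Sections 5.B.2 and 9.C contradict each other on the analysis set and the cut-off. If treatment reduces acquisition, the hazard ratio is biased upward, against treatment, by about 2% to 6% at the plan's rates. Larger shifts need acquisition well above the plan's 10% and reduced overall. With no effect on acquisition there is no bias. Direction and mechanism are firm. The size rests on assumed length of stay, infection rate and acquisition timing, none of which the plan gives for this trial. The contradiction between the sections stands whatever the size.

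**What to change.** Amend Sections 5.B.2 and 9.C before database lock and unmasking:

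1. In the pre-colonisation time-to-infection analysis, end time at the first of counted infection, first *S. aureus* acquisition, discharge or death, and call the result a cause-specific hazard ratio.
2. Exclude no randomised, baseline-negative neonate because of a later infection.
3. Use one cut-off date in both sections, and state that an infection whose own culture falls on or before that date counts.
4. Use the planned all-infections analysis, with time to infection, discharge or death, for the total treatment effect, including the 4- and 8-week risks.
5. State as a limitation that censoring at acquisition assumes colonisation and infection risk are independent given arm.
6. Say whether the 90-day limit of the primary analysis applies to infection.

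The cost is wording: Section 8 already collects culture, admission and discharge dates. The first analysis loses a little person-time, and dependence between colonisation and infection is only partly addressed there.

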**3. Eradication of *S. aureus* colonization in parents following treatment**

**Outcome ascertainment** – Parents will be monitored as described above in section 4.D to monitor *S. aureus* colonization over time. Parents will be tested at baseline, and then every two weeks for the first two months, if available, while neonate remains in the NICU, monthly starting on third month their neonate remains in the NICU, at the time the infant acquires *S. aureus* colonization in the NICU, and at time of discharge from the NICU for a neonate that did not acquire *S. aureus* colonization in the NICU.

#### **4. Natural history of *S. aureus* colonization in parents receiving placebo**

**Outcome ascertainment** – same as above for parents receiving placebo

#### **5. Adverse reactions to treatment**

**Outcome ascertainment** – Participants will be instructed to report any rash, blister, itching, redness, swelling or other skin irritation, swelling of the face or limbs, difficulty breathing or swallowing, and any significant discomfort or illness that occurs during treatment. Study staff will specifically ask for these symptoms during the 5-day treatment period and after the treatment period at Day 6, and will report any adverse event that is thought to be related to the study on the Adverse Event Log as well as any other perceived adverse events.

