**Mupirocin Ointment Possible Adverse Effects:** Local adverse effects may be associated with mupirocin application. Mupirocin ointment may cause itching, pain, stinging, and burning. Local effects from the nasal formulation have included epistaxis, rhinitis, taste perversion, pharyngitis, burning, and cough. Gastrointestinal side effects have included nausea (1.1%), abdominal pain (<1%), and diarrhea (<1%). Dry mouth has been reported with mupirocin nasal (<1%). Nervous system side effects associated with intranasal mupirocin have included headache (9%). Dizziness has been reported with mupirocin ointment (<1%). Ocular side effects associated with mupirocin nasal ointment have included blepharitis (<1%).

**Chlorhexidine Gluconate-impregnated Cloths Possible Adverse Effects:** The soap may cause burning and dryness of the skin. It may cause burning of the eyes, but it's not recommended to be used above the neck. Skin erythema and roughness, dryness,

sensitization, allergic reactions are possible, but rare.

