### **Adverse events collection and reporting**

As described above, participants on treatment will be instructed to report any rash, blister, itching, redness, swelling or other skin irritation, swelling of the face or limbs, difficulty breathing or swallowing, and any significant discomfort or illness that occurs during treatment. Study staff will specifically ask for these symptoms every day while monitoring compliance with treatment and will report any adverse event that is thought to be related to the study on the Adverse Event Log as well as any other perceived adverse events. Neonates will be monitored for Serious Adverse Events.

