Adverse events, as defined in Section 8, will be reported overall and separately by treatment group. Comparisons across treatment groups will be made using Fisher's Exact tests.

In addition, a series of planned secondary analyses will be conducted including subgroup analyses for the primary outcome, baseline-covariate adjusted analyses for the primary and secondary outcomes, per-protocol (PP) analyses for the primary and secondary outcomes and evaluation of patterns of loss and reacquisition of *S. aureus* among the parents (both treated and control).

Planned subgroup analyses include repeating the analysis for the primary outcome within strata defined by i) neonates with MRSA vs. those with MSSA, ii) collection site of colonization for the parent/caregivers, categorized as nares alone (i.e. all cultured parent/caregivers colonized in the nares) vs. nares + other (i.e. at least one parent/caregiver colonized in the nares) vs. non-nares; iii) LGA (large for gestational age) vs. SGA (small for gestational age); and iv) birthweight (< 1500g vs.  $\geq 1500$ g). The subgroup analyses will be based on Cox proportional hazards models that include a main term for treatment, a main term for subgroup (binary indicator) and the interaction between treatment and subgroup. Confidence intervals and the hypothesis test for no interaction will be derived based on the bootstrap procedure defined above.

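### The symptoms staff ask about by name are skin and allergic ones; nearly all listed mupirocin effects, including headache (9%), rest on a general prompt limited to significant complaints, so mild ointment effects are likely to be under-reported.

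*Combined protocol and SAP*

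**What the plan says.** Adverse reactions are a listed secondary outcome (Section 5.B.5). The list of symptoms has two parts. The first is specific: "Participants will be instructed to report any rash, blister, itching, redness, swelling or other skin irritation, swelling of the face or limbs". The second continues: "difficulty breathing or swallowing, and any significant discomfort or illness that occurs during treatment". Staff then prompt for the whole list: "Study staff will specifically ask for these symptoms during the 5-day treatment period and after the treatment period at Day 6". Section 8 (Adverse events collection and reporting) repeats the list and the daily prompt: "Study staff will specifically ask for these symptoms every day while monitoring compliance with treatment". Staff log events thought to be related to the study "as well as any other perceived adverse events".

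Section 6.A sets out what is expected of the ointment. For the nose and throat it says "Local effects from the nasal formulation have included epistaxis, rhinitis, taste perversion, pharyngitis, burning, and cough". It adds itching, pain and stinging, three gastrointestinal effects (nausea at 1.1%, the other two below 1%), dry mouth, dizziness and blepharitis (each below 1%), and headache at 9%.

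Section 8 defines an adverse event in parents broadly, as an unwanted and unusual symptom or sign. It has a Grade 1 for mild symptoms that interfere little or not at all with daily life. Section 9.C uses that definition: "Adverse events, as defined in Section 8, will be reported overall and separately by treatment group". Arms are compared with Fisher's exact tests.

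**The concern.** The named questions fit the cloths and allergic reactions. They do not fit the ointment's profile as the protocol describes it. A parent with a mild headache, a changed taste or a runny nose is not asked about it by name, and may answer no when asked about significant discomfort or illness. Under Section 8 that symptom would still be an adverse event.

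At stake is how the tolerability result can be read. Both parents are treated even if only one is colonized (Section 4.C.6), so some adults without detected colonization also use the ointment. If few nasal, gastrointestinal or neurological complaints are reported, the reader could not tell good tolerability from a question that did not reach mild events.

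**Working it through.** **Step 1: match the two lists.** Counting burning once, Section 6.A gives 16 distinct mupirocin effects. Each is compared with the items in Sections 5.B.5 and 8.

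| Group (Section 6.A) | Effects | Asked by name? |
|---|---|---|
| Local, ointment | itching | yes |
| Local, ointment | pain, stinging, burning | no; may partly fall under the skin-irritation item |
| Nose and throat | epistaxis, rhinitis, taste change, cough | no |
| Nose and throat | pharyngitis | no; may partly fall under difficulty swallowing |
| Gastrointestinal and mouth | nausea, abdominal pain, diarrhea, dry mouth | no |
| Neurological | headache (9%), dizziness | no |
| Eye | blepharitis | no; may partly fall under facial swelling |

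Named: 1 of 16. Not named: 16 − 1 = 15. On the most generous reading, crediting every partial overlap, 16 − 1 − 3 − 1 − 1 = 10 effects still have no specific prompt, and headache is one of them.

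**Step 2: compare the thresholds.** The skin items include an open category (other skin irritation) with no severity limit. The general item that must catch the other effects is limited to significant complaints. The Section 8 definition sets no such limit for symptoms, and Grade 1 expressly covers mild ones. So the prompt is narrower than the definition on which the Section 9.C comparison is built. The logging rule for other perceived events governs what is written down once known; it puts no question to the parent.

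**Step 3: what incomplete capture does to the comparison.** Let p1 and p0 be the true rates on active and placebo, and c the fraction captured, equal in both arms because participants and investigators are masked (Section 4.C.6) and the questions are the same.

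- Observed ratio: (c × p1)/(c × p0) = p1/p0, unchanged.
- Observed difference: c × (p1 − p0), reduced in proportion to c.
- Expected count per arm: n × p × c.

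**Step 4: illustration only.** From the documents: p1 = 9% (a background rate with no trial inputs behind it), about 400 pairs (Section 4.A), hence about 200 families per arm with one or two parents each, and two-sided 0.05. Assumed: p0 of 3% or 5%, the values of c, and independence between parents. Power is by exact enumeration of Fisher's test.

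| Parents per arm | p0 | c | Expected, active / placebo | Difference (points) | Power |
|---|---|---|---|---|---|
| 200 | 3% | 100% | 18 / 6 | 6.0 | 0.66 |
| 200 | 3% | 50% | 9 / 3 | 3.0 | 0.31 |
| 200 | 3% | 25% | 4.5 / 1.5 | 1.5 | 0.10 |
| 200 | 5% | 100% | 18 / 10 | 4.0 | 0.28 |
| 200 | 5% | 50% | 9 / 5 | 2.0 | 0.12 |
| 200 | 5% | 25% | 4.5 / 2.5 | 1.0 | 0.05 |
| 400 | 3% | 100% | 36 / 12 | 6.0 | 0.94 |
| 400 | 3% | 50% | 18 / 6 | 3.0 | 0.66 |
| 400 | 3% | 25% | 9 / 3 | 1.5 | 0.31 |
| 400 | 5% | 100% | 36 / 20 | 4.0 | 0.56 |
| 400 | 5% | 50% | 18 / 10 | 2.0 | 0.28 |
| 400 | 5% | 25% | 9 / 5 | 1.0 | 0.12 |

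The ratio stays at 9/3 = 3.0 or 9/5 = 1.8 throughout. Power falls in every block, but its level depends on the assumed placebo rate as much as on capture.

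**The case against.** The strongest reply is that the unnamed effects are not left out. The general item is part of the list staff put to parents daily and at Day 6. Staff also log other perceived events, the daily contact is meant to monitor for adverse events (Section 6.B), and at Day 6 parents are asked about ease of use and comfort (Section 5.B.6). The case report form and Day 6 questions are not in the documents and may be more detailed. All of this stands. A reader might infer that ointment effects are collected only by spontaneous report; the text does not support that. The contrast is between a named prompt and a general one.

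Second, a reader might infer a bias between arms. Masking and identical questions argue against it, and Step 3 shows the ratio is unaffected under equal capture.

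Third, Section 9.C specifies no test for headache or for ointment effects. Ointment and cloths are given together against a double placebo, so the arm comparison could not isolate the ointment under any checklist. That also stands, and it limits what the power figures mean.

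Fourth, Section 6.B says expected and unexpected events go to the DSMB. It does not promise that each expected effect is asked by name, so nothing there is breached.

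The threshold is what these replies leave untouched: a general question about significant complaints is a weaker net for mild events than the Section 8 definition calls for.

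**Conclusion.** The point holds as a weakness in ascertainment of a secondary safety outcome. Fifteen of 16 listed mupirocin effects (10 on the most generous reading) lack a specific prompt. Among them is headache, which has the highest frequency the protocol gives. They depend mainly on a general question with a higher threshold than the protocol's own adverse event definition. Mild ointment effects are therefore likely to be under-reported, giving lower absolute rates and less sensitivity in the Section 9.C comparison.

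The documents do not support a stated size for the shortfall or for the loss of power. They give no capture fraction and no placebo rate, and Step 4 shows only how the result moves with assumed values. The conclusion of no distortion in the ratio assumes equal capture in the two arms. The point does not touch the primary outcome. It is a cheap improvement worth making, not a correction of an error in the analysis.

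**What to change.** In Section 5.B.5 and in Section 8 (Adverse events collection and reporting):

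- Add to the solicited checklist: headache; nose bleed; rhinitis; nasal pain, stinging or burning; taste change; sore throat; cough; nausea; abdominal pain; diarrhea; dizziness; dry mouth; eyelid irritation.
- Ask it at the existing daily contacts and at Day 6, in the same words in both masked arms.
- Keep the open question, but without the restriction to significant complaints, so that it matches the Section 8 definition.

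In Section 9.C, state that solicited events will be tabulated by name and arm. If the case report form already lists these symptoms, it is enough for the protocol to say so.

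The cost is wording in the protocol and case report form and slightly longer contacts; no new visits, staff or participants are needed. The downside is that more mild, non-specific events will be recorded in both arms.
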